2.2. Endpoints

The primary study endpoint is posterior eyelid temperature (palpebral conjunctiva) using the ICI-7320 infrared camera (Infrared Cameras Inc., Beaumont, TX). This metric has been selected as the ICI-7320 is FDA-approved [510(k) clearance] for use in medical imaging of any part of the body's surface. Collection of surface temperature with infrared video will allow for capture of the inner eyelid temperature while eyelids are inverted to access the palpebral conjunctiva. Other observations endpoints are Topography, Tear Lipid Layer thickness and Non-invasive Tear Break Up Time after treatment.

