2.3. Hypotheses

1. After 12 minutes of treatment, the MiBo ThermoFlo will not heat the posterior eyelid palpebral conjunctiva to a temperature of 40°C.

Background: Ocular surface temperature is usually 34.03 ± 0.51 °C in the ‘normal’ eye. The temperature required to melt obstructive secretions in the Meibomian glands ranges from 32-45°C but the more severely obstructed glands present in MGD would require a temperature of >40°C, for effective treatment. There is an approximate 5°C difference in temperature between heat applied on the external eyelid surfaces and that which reaches the inner surface of the lids (palpebral conjunctiva), where the meibomian glands are located. This difference is due to both dissipation of heat while passing through the lid tissues and to constant movement of blood through vasculature wicking heat away from the lids. Therefore, achieving the desired temperature of 40°C at the palpebral conjunctiva requires a constant heat of at least 45°C be maintained on the outer lid surface, a temperature which may be both uncomfortable and risk causing thermal injury to the eyelid skin.

Other Observations

1. After 10 minutes of treatment, the Bruder Mask will not heat the posterior eyelid palpebral conjunctiva to a temperature of greater than 40°C.
2. There is no difference in posterior eyelid palpebral conjunctiva between the Bruder Mask and the MiBo ThermoFlo

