1.8	Eligibility after Baseline	All responses to Inclusion Criteria questions must be answered “yes” and all responses to Exclusion Criteria questions must be answered “no” for the subject to be considered eligible.	

Visit 1: Baseline			
Step	Procedure	Details	
		If subject is deemed to be ineligible after baseline, proceed to Final Evaluation and complete all forms.	

Visit 1: Treatment			
Step	Procedure	Details	
1.9	Eyelid Photography	The upper and lower eyelid margins of the subject will be photographed, OD, OS	Work Aid: Eyelid Photography
1.10	Tear Lipid Layer Thickness (LLT)	Measure the pre-treatment tear film LLT using the TearScience Lipiview, (OD, OS)	Work Aid: TearScience LipiView II Lipid Layer Thickness Measurement
1.11	Non-Invasive Tear Break Up Time (NITBUT)	Perform pre-treatment NITBUT using Oculus Keratograph 5 (OD, OS)	SOP_C12_Oculus Keratograph_V2
1.12	Corneal Topography	Perform pre-treatment corneal topography with the Oculus Keratograph	SOP_C12_Oculus Keratograph_V2
1.13	Thermography	Perform pre-treatment measurement of the external eyelid and palpebral conjunctival temperature for the upper and lower lids, (OD and OS)	SOP_C31_Thermography_V1.0
1.14	Randomization	Randomize treatment to eye using the randomization schedule	
1.15	MiBo ThermoFlo	Perform 12-minute MiBo ThermoFlo treatment on the eye indicated on the randomization schedule using the ThermoFlo Elite Eye Pad.	Work Aid: MiboFlo
1.16	Thermography	Immediately perform post-treatment measurement of the external eyelid and palpebral conjunctival temperature for the upper and lower lids, collecting data for the lower lid first.	SOP_C31_Thermography_V1.0
1.17	Bruder Mask	Heat the Bruder Mask per the manufacturer's instructions, measure the mask surface temperature and perform 10 minute Bruder Mask treatment on the contralateral eye.	Work Aid: Bruder Mask_V2

Visit 1: Treatment			
Step	Procedure	Details	
		Note: The Bruder Mask should be placed gently on the closed eyelids. Do not apply pressure on the mask and eye.	
1.18	Thermography	Perform post-treatment measurement of the external eyelid and palpebral conjunctival temperature for the upper and lower lids	SOP_C31_Thermography_V1.0
1.19	Tear Lipid Layer Thickness (LLT)	Measure the post-treatment tear film LLT using the TearScience Lipiview, OD, OS	Work Aid: TearScience LipiView II Lipid Layer Thickness Measurement

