14. STATISTICAL METHODS

14.1. General Considerations

Statistical Analysis will be undertaken by the sponsor or under the authority of the sponsor. A general description of the statistical methods to be implemented in this clinical trial is outlined below.

All data summaries and statistical analyses will be performed using the SAS software Version 9.4 (SAS Institute, Cary, NC). Throughout the analysis of data, the results for each subject/eye will be used when available for summarization and statistical analysis. Unscheduled visits will be summarized separately and will be excluded from the statistical analysis.

Summary tables (descriptive statistics and/or frequency tables) will be provided for all baseline variables, efficacy variables and safety variables as appropriate. Continuous variables will be

summarized with descriptive statistics (n, mean, standard deviation (SD), median, minimum and maximum). Frequency count and percentage of subjects or eyes within each category will be provided for categorical data.

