14.5. Primary Analysis

Eyelid Temperature will be analyzed using a linear or generalized linear mixed model depending on the distribution of temperatures. Treatment sequence, treatment, eyelid location (inner and outer) and the interaction between treatment and eyelid location will be included as fixed effects. Age and gender may also be included as covariates when necessary. Subject will be included as a random effect. An appropriate covariance structure will be used to model the residual errors between measurements within same subject across eyes (R-side). The covariance structure will be selected based on the finite-sample corrected Akaike's Information Criterion. Covariance structures considered include:

- Unstructured Covariance Structure (UN)
- Homogenous Compound symmetry (CS)

Comparisons between the two treatments will be carried out using two-sided 95% confidence intervals constructed for least-square mean differences (MiBo ThermoFlo minus Bruder mask).

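### The primary model in section 14.5 has no eye-within-subject effect; if both lids are entered with CS residuals, eye-level variance makes the palpebral MiBo minus Bruder 95% CI too narrow

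*Combined protocol and SAP*

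**What the plan says.** Section 5.1 randomises eyes within a subject, so the eye is the treated unit. In section 7.2, step 1.16 takes external and palpebral temperatures after MiBo "for the upper and lower lids, collecting data for the lower lid first". After the Bruder mask, step 1.18 asks staff to "perform post-treatment measurement of the external eyelid and palpebral conjunctival temperature for the upper and lower lids" and sets no order. That is four post-treatment readings per eye and eight per subject.

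Section 14.5 fits sequence, treatment, location (inner or outer) and treatment by location as fixed effects. "Subject will be included as a random effect". For the residuals, "An appropriate covariance structure will be used to model the residual errors between measurements within same subject across eyes (R-side"). The candidates are UN and "Homogenous Compound symmetry (CS"), chosen by AICc. The planned inference is a two-sided 95% interval for the MiBo minus Bruder difference. Section 14.1 adds only that "the results for each subject/eye will be used when available for summarization and statistical analysis". No section says whether upper and lower lids are averaged, selected or both entered, what the repeated index is, or which df method applies.

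The palpebral surface is the one that matters: "The primary study endpoint is posterior eyelid temperature (palpebral conjunctiva) using the ICI-7320 infrared camera" (section 2.2). Section 2.3 puts the comparison of devices under Other Observations: "There is no difference in posterior eyelid palpebral conjunctiva between the Bruder Mask and the MiBo ThermoFlo".

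**The concern.** The error for a MiBo minus Bruder contrast must include variation between the two eyes of a subject. Under CS with both lids entered, all readings in a block share one correlation. Whatever is common to one treated eye is then left out of the standard error, and the interval is too narrow.

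The documents show one possible source. The Bruder work aid lets the mask go on at any temperature from 37 to 42 °C, which would act on every reading of that eye.

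A second omission can pull the other way. Without a lid term, an upper/lower difference may go into the residual and widen the interval.

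This interval is the only inference that section 14.5 plans. Section 14.4 sets an overall type I error of 5%, and section 14.2 wants the data for later sample sizes, which needs a correct eye-level standard error.

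**Working it through.** **Inputs.** The plan gives n = 12 (minimum completers) to 20 (target), eight readings per subject and a 95% interval. It states no SD, correlation or power, so there is no planned figure to reproduce. Assumed: within-subject variance scaled to 1, eye share a = 0.3, 0.5 or 0.7, reading error e = 1 − a, and a lid shift d in SDs of a single reading within subject.

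**True variance.** For the palpebral difference with the lids averaged, n × Var = 2a + e = 1 + a, that is 1.3, 1.5 and 1.7.

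**What each CS fit estimates, n = 12, d = 0.** With both lids entered, the model takes n × Var to be the residual variance s². Its expectation is:
- Whole-subject block (81 df): [11(4a + e) + 70e]/81. At a = 0.5: (11 × 2.5 + 70 × 0.5)/81 = 0.772; SE ratio √(0.772/1.5) = 0.717.
- Subject-by-location block (70 df): [22(2a + e) + 48e]/70. At a = 0.5: (22 × 1.5 + 48 × 0.5)/70 = 0.814; SE ratio 0.737.
- Eye-pair block (subject by location by lid, 46 df): [24 − (1 + a)]/23. At a = 0.5: 22.5/23 = 0.978; SE ratio 0.808.

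With lids averaged and a whole-subject block (33 df), the model takes n × Var to be 2s², with E(s²) = [11(2a + e/2) + 22e/2]/33. At a = 0.5: 2 × 0.583 = 1.167; SE ratio 0.882.

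**Simulated coverage, n = 12, d = 0.**

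| Reading of 14.5 | a = 0.3 | 0.5 | 0.7 |
|---|---|---|---|
| Both lids, CS, whole subject | 89% | 84% | 78% |
| Both lids, CS, subject by location | 90% | 85–86% | 80% |
| Both lids, CS, eye pair | 91% | 89% | 85–86% |
| Lids averaged, CS, whole subject | 93% | 91–92% | 90% |
| Lids averaged, CS, subject by location | 94–95% | 94–95% | 94–95% |
| Lids averaged, 4×4 UN (n − 1 df) | 94–95% | 94–95% | 94–95% |
| Paired t on eye means | 95% | 95% | 95% |

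The CS results with both lids entered are nearly the same at n = 20. At a = 0 and d = 0 the whole-subject fit covers 95%, as it should.

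**Selection by AICc.** With both lids entered, UN has 36 parameters. Its penalty at n = 12 is 2 × 36 × 91/54 = 121.3, against 4 × 91/88 = 4.1 for CS. UN was picked in 0, 1 and 9% of runs at n = 12 and in 1, 14 and 73% at n = 20. Coverage after selection was 89/84/77% and 89/82/86% (600 runs each, about ±3 points).

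**Lid shift.** A shift common to both eyes adds 2nd² to the residual sum of squares under the whole-subject and subject-by-location blocks. With a = 0 and a whole-subject block, s² becomes 1 + 24/81 = 1.30 at d = 1 and 1 + 96/81 = 2.19 at d = 2; coverage is about 97% and 99.6%. Under an eye-pair block this shift cancels.

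A shift in one eye only, as the reading order could cause, adds nd² under the whole-subject block. Then s² is 1 + 12/81 = 1.15 and 1 + 48/81 = 1.59, with coverage of about 96.5% and 98.4–98.8%.

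At a = 0.5 under the whole-subject block, the two errors offset at a common shift of √(0.728 × 81/24) = 1.57 SD, or a one-eye shift of √(0.728 × 81/12) = 2.22 SD.

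**Mask window alone.** A uniform start over 37–42 °C has SD 5/√12 = 1.44 °C. If 10, 25 or 50% of this reaches the lid and the reading SD is 0.5–1.0 °C (all assumed), the eye share is 0.01–0.04, 0.06–0.21 or 0.21–0.51. Coverage with both lids under whole-subject CS is then 94–95, 91–94 or 84–91%.

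**The case against.** The strongest reply is that the large losses need a reading the documents do not state. Location has two levels in section 14.5, and section 14.1 speaks of results per subject and eye, so one inner and one outer value per eye is a fair reading. With lids averaged, a subject-by-location block or a 4×4 UN is sound. Even whole-subject CS covers 92–94% after AICc selection. Section 14 calls itself a general description, and its list of structures need not be exhaustive. This stands as a limit on size. It does not remove the problem, because the text permits sound and unsound analyses alike and does not choose.

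It is also fair that an eye share of 0.7 has no documentary basis, and that the mask window by itself may matter little.

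A reader might infer that the missing lid term always widens the interval. It does not: a common shift cancels under an eye-pair block. The order difference between steps 1.16 and 1.18 is a treatment-by-lid effect, which widens less than a common shift under whole-subject CS and which a lid main effect alone would not remove.

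**Conclusion.** The concern holds conditionally. If both lids are entered with CS residuals and eyes within a subject differ, the palpebral interval is too narrow unless a lid shift happens to offset it. For eye shares of 0.3 to 0.7 and no lid shift, coverage runs from about 91% down to 78%, depending on share and block. Larger enrolment does not help under CS, and AICc does not reliably rescue it. With lids averaged and whole-subject CS the loss is about 2 to 5 points before selection.

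The shares and shifts are assumptions; section 14.2 confirms that no earlier data exist for this camera.

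Two stronger readings should be resisted. A reader might infer that the planned interval is simply invalid, but some permitted versions are sound. A reader might also infer that the 40 °C hypothesis is undermined, but this interval does not test it, and section 2.3 lists the device comparison under Other Observations. The point should be fixed before analysis; it is not a fatal flaw.

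**What to change.** State that the device comparison is the palpebral MiBo minus Bruder difference, and obtain it in one of two ways.

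1. Average the upper and lower palpebral readings within each eye and report a paired t interval on the within-subject difference. Coverage is about 95% in every scenario examined.
2. Keep the mixed model, drop the R-side CS/UN choice, and add a random eye-within-subject effect plus lid and treatment-by-lid fixed effects, with Kenward-Roger df. Add a random eye-by-location effect if the eye effect may differ between surfaces. A check with the eye effect and a lid main effect (Satterthwaite df, treatment-by-lid term not included) covered 94.7–95.6% for shares of 0.1 to 0.75, and 95.7–96.4% with no eye variance.

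If the R-side choice is kept, average the lids and state the block, repeated index and df method; whole-subject CS should not remain a candidate.

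The cost is a few lines of text and code. With no eye or lid effect, the paired multiplier at n = 12 is 2.20 (11 df) against 1.99 (81 df), about 11% wider; at n = 20 it is about 6% wider. The paired option drops any subject with only one eye measured, since section 14.9 does not impute; the mixed model keeps them.

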Study Responsible Clinician	<hr/> 
See Electronic Signature Report [name], OD Principal Research Optometrist
	<hr/> 
DATE

Clinical Operations Manager	<hr/> 
See Electronic Signature Report [REDACTED] Clinical Operations Department
	<hr/> 
DATE

Biostatistician	<hr/> 
See Electronic Signature Report [REDACTED] Biostatistician II, Clinical Sciences
	<hr/> 
DATE

Biostatistics Reviewer	<hr/> 
See Electronic Signature Report [REDACTED]. Senior Manager of Biostatistics, Clinical Sciences
	<hr/> 
DATE

Data Management	<hr/> 
See Electronic Signature Report [REDACTED] Clinical Project Manager – Data & Systems, Clinical Operations
	<hr/> 
DATE

Approver:	<hr/> 
See Electronic Signature Report [REDACTED] Director of Global Medical Affairs
	<hr/> 
DATE

CHANGE HISTORY

Version	Originator	Description of Change(s) and Section Number(s) Affected	Date
1.0	[name] & [name]	Original Protocol	01 OCT 2018
2.0	[name]	
Clarification for treatment of Bruder MaskUpdate to Section 2.2Topography added to Table 3	15 NOV 2018

[figure not shown]
SYNOPSIS

Protocol Title	MiBo ThermoFlo Lid Temperature Evaluation
Sponsor	JJVC, [name]
Clinical Phase	Phase 4
Trial Registration	This study will be registered on ClinicalTrials.gov by the Sponsor
Test Article(s)	Investigational Product: MiBo ThermoFlo Control Product: Bruder Moist Heat Single Eye Compress
Wear and Replacement Schedules	N/A
Objectives	
Determine anterior and posterior eyelid temperature after use of the MiBo ThermoFlo following standard clinical protocol and evaluate changes to the tear film with one MiBo ThermoFlo treatment session.
 
Primary Objective: Determine the temperature of the palpebral conjunctiva after MiBo ThermoFlo treatment and Bruder Mask (i.e. hot compress) treatment using the ICI-7320 infrared camera (Infrared Cameras Inc., Beaumont, TX)
 
Secondary Objectives: Tear Film Lipid Layer Thickness and Non-Invasive Tear Break Up Time post treatment

Study Endpoints	
Primary endpoint(s): Palpebral Conjunctival Temperature
 
Secondary endpoint(s): Tear Film Lipid Layer Thickness, Non-invasive tear break up time (NITBUT)

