2. STUDY OBJECTIVES, ENDPOINTS AND HYPOTHESES

2.1. Objectives

The primary study objective of this pilot study is to measure posterior eyelid temperature (palpebral conjunctiva) to determine the ability of the MiBo ThermoFlo to raise posterior eyelid temperature to levels sufficient to provide a therapeutic effect in the treatment of MGD.

Other observations in this study include testing whether the MiBo ThermoFlo treatment can induce a change in tear lipid layer thickness and/or non-invasive tear break up time after (1) 12-minute treatment session.

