14.2. Sample Size Justification

Inner eyelid palpebral temperature has not previously been collected with the ICI-7320 infrared camera (Infrared Cameras Inc., Beaumont, TX) and a search of the peer reviewed literature failed to show published results with the device. Previous evaluations of inner eyelid temperature have focused primarily on the lower eyelid using infrared pyrometers. Given the lack of previous data, a formal sample size calculation cannot be completed. The sample size selected approaches the sample size required to meet the Central Limit Theorem and provide data for future sample size calculations.

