Note: If you are using the capture image series option and need to stop image capture, click on the black box icon immediately to the right of the red recording icon directly beneath the active image:

11. Captured images will appear in the lower left-hand side of the screen. Click on the images to save and then click on "Save Image". To save all images, click on "Save All". Save images under a file name specific for the particular study and subject (and eye, if both eyes are evaluated).
12. Repeat Steps 6-9 above for the fellow eye.

Note: DO NOT unplug the USB cable from the camera or computer as this may affect calibration, particularly the emissivity correction (which is set to 0.98 as the surface of the human skin has a emissivity of 0.97-1.00; a value of 1.00 is a perfect radiator, or black body). To check for this, click on the Temperatures tab and select "Emissivity Correction".

D. Procedure: Data Backup

1. Data should be backed up after each subject has been completed but at least once per day.
2. Copy files requiring backup: Click on the icon "Shortcut to My Passport" which is located on the desktop.
3. Check to be sure the files have indeed been transferred to the My Passport external hard drive.

E. Procedure: Image Analysis

1. Under the File tab, select the "Load Image" option.
2. Select the area of the image to be analyzed using the options (box, circle, point, line, or none) located in the Analysis box located at left-hand margin of the screen (yellow arrow, Fig. 3).

UNIVERSITY of HOUSTON

THE OCULAR SURFACE INSTITUTE

Noncontact Infrared Thermography

3. Click the image immediately to the right and click the area where you would like to evaluate the surface temperature. The option selected (i.e., box) will show up on the image. This is called a Zone. You can also click on other areas of the image to introduce new zones or select another analysis (i.e., circle) to introduce a new zone shape to the image for surface temperature analyses within separate areas of the image. Each Zone will be designated in numerical order (see Fig. 3).
4. Use the red boxes to widen the area of analysis as needed.
5. The results of the minima and maxima surface temperature along with the standard deviation in the designed area of analysis will show at the right-hand side of the screen about midway down (green arrow, Fig. 3). Transfer data points into an Excel spreadsheet for additional analyses (i.e., statistical analyses).

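### The hypothesis is about MiBo reaching 40°C at the inner lid, but the only planned inference is MiBo minus Bruder, which cannot answer it

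*Combined protocol and SAP*

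**What the plan says.** - **Hypothesis (2.3).** One item is numbered as the hypothesis: "After 12 minutes of treatment, the MiBo ThermoFlo will not heat the posterior eyelid palpebral conjunctiva to a temperature of 40°C". The statement that the two devices do not differ comes second under the separate label of other observations. The first item there sets Bruder against 40°C.
- **Objective (2.1).** The study is "to determine the ability of the MiBo ThermoFlo to raise posterior eyelid temperature to levels sufficient to provide a therapeutic effect". Section 1 puts that level at about 40°C at the inner lid.
- **Synopsis primary objective.** "Determine the temperature of the palpebral conjunctiva after MiBo ThermoFlo treatment and Bruder Mask" treatment, which asks for an estimate per device.
- **Primary analysis (14.5).** A mixed model with sequence, treatment, location (inner or outer) and treatment by location. The only inference stated is "Comparisons between the two treatments will be carried out using two-sided 95% confidence intervals constructed for least-square mean differences (MiBo ThermoFlo minus Bruder mask". The location at which the contrast is taken is not given.
- **Other parts of Section 14.** 14.1 plans descriptive statistics without an interval. 14.4 sets an overall 5% type I error rate. 14.6 and 14.7 are not applicable. None of them mentions 40°C.
- **Measurement.** Step 1.16 in 7.2 records "palpebral conjunctival temperature for the upper and lower lids, collecting data for the lower lid first". The thermography SOP (Appendix D, image analysis, step 5) describes its output as "The results of the minima and maxima surface temperature along with the standard deviation in the designed area of analysis".

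**The concern.** The plan gives formal inference to a question it ranks as an observation and none to the question it ranks as the hypothesis. A claim that MiBo does or does not reach 40°C would rest on reading a mean or a maximum from a descriptive table. It would have no planned interval and no prior statement of what counts as not reaching 40°C: a mean below 40, an upper limit below 40, or no eye at 40.

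The quantity to compare with 40°C is also open. Two lids are measured, and the SOP reports a zone minimum and a zone maximum, which can fall on opposite sides of 40°C. The study is unmasked (5.2), and the protocol states the expected result in advance (Sections 1 and 4.2). If these choices are made after the data are seen, the answer is open to challenge.

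**Working it through.** The plan states no power and no formula-based sample size (14.2), so there is no planned figure to reproduce.

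**1. The contrast carries no information on the level.** Let the inner-lid means be M (MiBo) and B (Bruder). Adding a constant c to both gives (M + c) − (B + c) = M − B, so neither the estimate nor its interval moves. One simulated set of 12 pairs shows this:

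| Both true means | 95% CI, MiBo minus Bruder | 95% CI, MiBo mean |
|---|---|---|
| 37°C | −0.37 to 0.85 | 36.85 to 37.62 |
| 41°C | −0.37 to 0.85 | 40.85 to 41.62 |

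The planned result is identical in both rows, and the answer to the hypothesis is opposite. This step needs no assumption about the SD.

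**2. What an interval against 40°C would give.**

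Inputs:
- n = 12 (minimum completing) and n = 20 (target enrollment), from 4.3.
- Threshold 40°C, from 2.3.
- SD of post-treatment inner-lid temperature: not given, so assumed at 1, 2 and 3°C. The only related figure is ±0.51°C for the normal ocular surface (2.3), an imperfect proxy.
- One value per eye, with a one-sample t interval approximating the model's least-squares mean.

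Half-width = t(0.975, n−1) × SD/√n:
- n=12: 2.201/√12 = 0.635 × SD
- n=20: 2.093/√20 = 0.468 × SD

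For the upper limit to fall below 40°C, the observed mean must be below 40 − half-width. The probability of that comes from the noncentral t. At n=12:

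| SD (°C) | Half-width (°C) | Observed mean must be below | Probability, true mean 37°C | Probability, true mean 39°C |
|---|---|---|---|---|
| 0.51 | 0.32 | 39.68 | >99.9% | >99.9% |
| 1 | 0.64 | 39.36 | >99.9% | 88% |
| 2 | 1.27 | 38.73 | 99.7% | 35% |
| 3 | 1.91 | 38.09 | 88% | 18% |

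At n=20, SD 2 and a true mean of 39°C, the probability is 56%.

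The protocol's own figures, a pad at about 42°C (Section 1) and a loss of about 5°C through the lid (2.3), imply 42 − 5 = 37°C at the inner lid. There the planned sample would usually be informative.

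**3. The mean and the individual eye are different questions.** At mean 38°C and SD 2, with a normal distribution assumed, the share of eyes at or above 40°C is 1 − Φ((40 − 38)/2) = 1 − Φ(1) = 16%. If no eye reaches 40°C, the exact two-sided 95% upper bound on the share is 1 − 0.025^(1/n), which is 26% for 0 of 12 and 17% for 0 of 20.

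**4. Camera accuracy.** The ICI 7320 sheet gives ±1°C or ±1%. The 510(k) summary for the camera family gives 2°C or 2%. If the tolerance acted wholly as a shared offset (an assumption), the bar becomes 39 or 38°C. At a true 37°C and n=12, the conclusion survives a 1°C offset with probability 88% (SD 2) or 56% (SD 3), and a 2°C offset with probability 35% or 18%. At SD 0.51 it survives either in more than 99.9%.

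**The case against.** The strongest reply is that this is a pilot. Section 14.2 says no formal calculation is possible and that the data are to "provide data for future sample size calculations". The synopsis objective is descriptive and is largely met by the 14.1 summaries. A reader can build an interval from n, mean and SD, and a maximum below 40°C answers the hypothesis literally for the eyes observed. The MiBo inner-lid mean can also be obtained from the planned model. If the true mean is near 37°C, the practical ambiguity may be small, and the less favourable probabilities depend on assumed SDs of 2 or 3°C.

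Much of this is fair. Information on 40°C will exist, a powered test is not required, and the SD range is illustrative. What is missing is a pre-specified interval and a rule for reading it. The plan still states a numbered hypothesis and a 5% error rate, and 14.5 does not call for the estimate that its own model could supply.

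The SOP's output list may be incomplete, because it refers to a figure that is not shown and elsewhere says the software can give an overall surface temperature. That is a further reason to name the statistic. The camera point is a sensitivity question, separate from the mismatch in 14.5.

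**Conclusion.** The concern holds and should be fixed before analysis. The primary analysis in 14.5 cannot support or reject the hypothesis in 2.3, whatever the sample size or SD, because the contrast is unaffected by the level both devices reach. The Bruder statement against 40°C has no planned inference either.

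How decisive a proper interval would be depends on figures the documents do not give. With one value per eye and SD from 1 to 3°C at n=12, the chance of showing a mean below 40°C is 88% to more than 99.9% at a true 37°C, and 18% to 88% at a true 39°C.

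**What to change.** In 14.5:

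1. Make the primary estimate the MiBo post-treatment least-squares mean at the palpebral conjunctiva, from the treatment-by-location model, with its two-sided 95% CI.
2. Name in advance the lid (upper, lower or both combined) and the zone statistic. The model has no upper/lower term, so if both lids enter as separate values, state how they are combined or add a term.
3. State the rule: the hypothesis is supported only if the upper limit is below 40°C, and is otherwise reported as not shown.
4. Report the number of MiBo eyes at or above 40°C with an exact CI, and the same quantities for Bruder.
5. Keep MiBo minus Bruder at the inner lid as a supporting estimate with its CI. Say that an interval including zero will not be read as showing no difference.
6. Add a sensitivity statement on whether the conclusion survives a shared camera offset of the stated accuracy. This should not be a mandatory margin.

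**Cost.** SAP wording, some extra model output and a simple exact count, with no added subjects or procedures. The downside is that the result may be inconclusive when the true mean is close to 40°C and the spread is wide (35% chance of support at 39°C with SD 2 and n=12), and the camera statement may weaken it further.
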